4.3. Justification for Dose

First-in--human dose selection was based on PK data collected from a wild-type mouse study; rat and monkey dose range finding studies; 4-week GLP toxicology studies in rats and monkeys; and efficacy data from 2 Akp2GW -/- mouse efficacy studies. A model-based approach employing dose response and population PK (PopPK) models was used to characterize the SC dose (15 mg [0.15 mL], 45 mg [0.45 mL], and 90 mg [0.90 mL]) after performing body weight-based forecasting to humans for the FIH study. A NOAEL based approach was used to determine the starting dose (15 mg IV). A summary of the expected exposure margin and- expected percentage of population with normalized mineralization response in humans for ALXN1850 is provided in Table 5. Given previous experience with asfotase alfa, it is expected that the ALXN1850 safety multiple will support flat dosing. The trade-off of flat dosing versus mg/kg dosing is some increase in PK variability (within a cohort) with a gain of reduction in potential errors in dosing and operational factors.

The 15 mg IV starting dose is considered the maximum recommended starting dose (MRSD). The starting dose was selected based on NOAEL from the 4-week GLP toxicology study in monkeys dosed SC q3d. Monkey was selected because it has relevant biology with humans. The monkey NOAEL was determined to be 20 mg/kg/q3d or 46 mg/kg/week. Assumptions of 1) no allometric scaling for a molecule with molecule weight > 100 kDa (Food and Drug Administration (FDA) guidance: Estimating the Maximum Safe Starting Dose in Initial Clinical Trials for Therapeutics in Adult Health Volunteers, 2005), 2) applying safety factor of 150, and 3) SC bioavailability (75%), 4) adult body weight of 70 kg, were factored into the calculation of the starting dose. Based on dose simulation results, the observed exposure of the NOAEL at 20 mg/kg/dose from the GLP monkey toxicity study is approximately 113-fold of projected exposure from the 15 mg IV starting dose (Table 5).

Cohort 1 will receive 15 mg as a single IV dose, followed by 15 mg SC at 1-week intervals for 3 doses. The 15 mg SC dose was calculated (based on dose-response modeling of mouse data) to produce normalized bone mineralization in 66% of a treated population.

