The protocol was amended to address the recommendation from the FDA to add a PK sample collection timepoint at the end of infusion for IV doses. Additional changes to assist recruitment/reduce participant burden were made, and the SoA tables were revised to ease readability. The clarifications in the IRB-approved Administrative Change Letters were incorporated. Additional minor changes were made in the amendment for clarification, consistency, and accuracy.

Section	Description of Change	Brief Rationale and/or Clarification
Section 1.1 Synopsis	Designated Day 65 (1st participant)/	Alexion decided the End-of-Treatment
Section 1.2 Study Schema	Day 57 (subsequent participants) as	Visit should be the last critical PK/PD
Section 1.3 Schedule of Activities	the End-of-Treatment Visit, which will now be considered the end of the	timepoint (5.5 half-lives for study drug)
1100111000		that is also sufficient for safety follow-
Section 7.2 Participant	Treatment Period (added to all except	up
Discontinuation/Withdrawal	Sections 7.2 and 9.2)	
from the Study	Added to all except Section 1.2 that	
Section 9.2 Sample Size	participants who withdraw/are	
Determination	withdrawn from the study following	
	completion of end-of-treatment	

Changes to the protocol in Amendment 4 are detailed below.

Section	Description of Change	Brief Rationale and/or Clarification
	procedures will be considered "completed" if they completed all prior PK/PD sampling within window and received all doses per the SoA. "Completed" participants do not need to be replaced.	
Section 1.1 Synopsis Section 1.3 Schedule of Activities	Permitted visit windows for the last 3 study visits were expanded from ± 1 day to ± 3 days (Day 51 [1st participant]/Day 43 [subsequent participants]), -3/+ 7 (EoT), -7/+14 days (EoS) Recalculated the planned study duration, including the period lengths comprising duration, due to these window changes	Expanding these windows is not expected to impact PK, PD, or safety assessments, and should reduce participant burden and drop-out tendency towards the end of this study
Section 1.1 Synopsis	Changed "Four participants will be assigned to each of the 3 cohorts (Cohorts 1, 2, and 3)" to "Five participants will be assigned to each of the 3 cohorts (Cohorts 1, 2, and 3)"	Four participants per cohort does not accommodate for potential dropouts. Total numbers have not changed (15 participants must be enrolled to complete at least 9)

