8.2. Plasma Pharmacokinetic Concentrations

Blood samples for analysis of concentrations of ALXN1850 in plasma for each of the treatments will be collected at the following time points:

First participant within each cohort	Subsequent participants within each cohort
Day 1: pre-dose, EOI, and 2h, 6h,, and 12h	Day 1: pre-dose, EOI, and 2h, 6h,, and 12h
post dose (IV dose)	post dose (IV dose)
Day 2 (24 hours post IV dose)	Day 2 (24 hours post IV dose)
Day 3 (48 hours post IV dose)	Day 3 (48 hours post IV dose)
Day 5 (96 hours post IV dose)	Day 5 (96 hours post IV dose)
Day 8 (168 hours post IV dose)	
Day 15: pre-dose and 2h, 6h, and 12h post	Day 8: pre-dose and 2h, 6h, 8h, and 12h post
dose (SC dose 1)	dose (SC dose 1)
Day 16 (24 hours post SC dose 1)	Day 9 (24 hours post SC dose 1)
Day 17 (48 hours post SC dose 1)	Day 10 (48 hours post SC dose 1)
Day 19 (96 hours post SC dose 1)	Day 12 (96 hours post SC dose 1)
-	
Day 22: pre-dose and 2h, 6h, and 12h post	Day 15: pre-dose and 2h, 6h, and 12h post
dose (SC dose 2)	dose (SC dose 2)
Day 23 (24 hours post SC dose 2)	Day 16 (24 hours post SC dose 2)

Page 12 of 29

Day 29: pre-dose and 2h, 6h, and 12h post	Day 22: pre-dose and 2h, 6h, and 12h post
dose (SC dose 3)	dose (SC dose 3)
Day 30 (24 hours post SC dose 3)	Day 23 (24 hours post SC dose 3)
Day 31 (48 hours post SC dose 3)	Day 24 (48 hours post SC dose 3)
Day 36 (168 hours post SC dose 3)	Day 29 (168 hours post SC dose 3)
Day 51 (3 weeks post SC dose 3)	Day 43 (3 weeks post SC dose 3)
Day 65 (5 weeks post SC dose 3)	Day 57 (5 weeks post SC dose 3)
Day 85 (8 weeks post SC dose 3)	Day 78 (8 weeks post SC dose 3)

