8.3. Plasma Pharmacokinetic Parameters

The plasma concentration-time data for ALXN1850 will be analyzed by non-compartmental analysis using Phoenix® WinNonlin® Version 8.0 or higher (Certara USA, Inc., Princeton, New Jersey). The following PK parameters will be derived for ALXN1850 based on actual date and times calculated relative to the actual date and time from the start of dose administration (for example, start of infusion) in each dosing period, where data permit. If missing actual sampling dates and times, then the nominal time relative to the start time of the administration will be used.

C _{max}	Maximum observed plasma concentration
C _{max_corrected}	Maximum observed plasma concentration (for SC dose only if carryover from IV exposure is observed)
C _{trough}	Trough (predose) concentration observed at the start of the dosing interval (C _{trough})
T _{max}	Time of maximum observed concentration
AUCt	Area under the curve (AUC) from time 0 to the last quantifiable concentration, calculated using the linear trapezoidal rule
AUC _{168h}	Area under the curve (AUC) from time 0 to 168h, calculated using the linear trapezoidal rule (for IV dose only)
AUC _{inf}	AUC from time 0 extrapolated to infinity, calculated using the linear trapezoidal method (IV dose only)
AUC _{tau}	AUC within the dosing interval, calculated using the linear trapezoidal method (SC dose only)
AUC _{tau_corrected}	AUC within the dosing interval, calculated using the linear trapezoidal method (for SC dose only if carryover from IV exposure is observed)
t _{1/2}	Apparent terminal elimination half-life, calculated as: ln (2) / Kel
CL	Total body clearance calculated as: Dose / AUC _{inf} (For IV dose only)
CL/F	Apparent total body clearance calculated as: Dose / AUC _{tau} at steady state (For SC dose and only if C _{trough} can attain steady state)
V_d	Volume of distribution during the terminal phase, calculated as: Dose / $[\lambda_z * AUC_{inf}]$ (For IV dose only)
V _d /F	Apparent volume of distribution during the terminal phase, calculated as: Dose / [λ_z * AUC _{tau} at steady state] (For SC dose and only if C _{trough} can attain steady state)
R	Subcutaneous accumulation ratio (AUC _{tau_SC} 3rd dose / AUC _{tau_SC} 1st dose)
F	Absolute bioavailability after subcutaneous administration, $F = AUC_{tau}$ (SC) / AUC_{inf} (IV)

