In addition to the above PK parameters, which will be listed and summarized, the following parameters will also be listed to document the selection of data points used to estimate $T_{1/2}$ using non-compartmental procedures:

λ_z	Terminal phase elimination rate constant
Number points	Number of data points used to estimate λ_z ; a minimum of 3 data points must be used, and C_{max} must not be included
λ_z lower	Lower bound used for the estimation of λ_z
λ_z upper	Upper bound used for the estimation of λ_z
Rsq	r^2 , the coefficient of determination (goodness of fit statistic); λ_z and all associated parameters will only be reported where $r^2 \ge 0.80$
%AUC _{extrap}	Percentage of AUC_{inf} due to extrapolation; If % $AUC_{extrap} > 20\%$ then, AUC_{inf} , CL, and V_d , will not be summarized

Additional plasma PK parameters may be calculated if deemed appropriate.

Plasma PK parameters for ALXN1850 will be presented in data listings and summarized separately using descriptive statistics (n, arithmetic mean, SD, %CV, geometric mean, geometric %CV, median, minimum, and maximum) by treatment. T_{max} will be summarized using the descriptive statistics median, minimum, and maximum only. Plasma PK will be presented by ADA status in figures. In addition, the Plasma PK parameters and ADA titers will be presented in the overlay figures for each subject overtime.

Plasma PK parameters of ALXN1850 will be reported to 3 significant figures in summary statistics except for %CV which will be reported to 1 decimal place and N and n which will be reported as integers.

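### Most IV profiles stop at 168 h, about 1.1 implied half-lives, so AUCinf will probably breach the SAP's 20% extrapolation limit, yet SAP 8.4 uses AUCinf without that limit

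*SAP*

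**What the plan says.** - **Parameters (SAP 8.3).** AUCinf is "AUC from time 0 extrapolated to infinity, calculated using the linear trapezoidal method (IV dose only"). CL is Dose/AUCinf and Vd is Dose/(λz × AUCinf), both for the IV dose only. F is AUCtau(SC)/AUCinf(IV).
- **Quality rules (SAP 8.3).** For λz, "a minimum of 3 data points must be used, and" Cmax is left out; r² must be at least 0.80. No minimum time span is set. If extrapolation exceeds 20%, AUCinf, CL and Vd "will not be summarized". The SAP does not say whether this applies profile by profile.
- **Use (SAP 8.4).** A power model is fitted to Cmax, AUC168h and AUCinf for IV and to AUCtau for SC. Dose proportionality is concluded if the 90% CI of the slope lies inside a stated interval. The bioavailability ANOVA compares AUCtau of the first SC dose with AUCinf of the IV dose. Neither analysis repeats the 20% condition or names a fallback.
- **Sampling (SAP 8.2; Protocol Table 3).** Subsequent participants are dosed on Days 1, 8, 15 and 22. Their last IV sample is the predose one in "Day 8: pre-dose and 2h, 6h, 8h, and 12h post" dose, at 168 h. The first participant in each cohort is dosed on Days 1, 15, 22 and 29, and so has IV samples at 168 h and 336 h.
- **Half-life.** None is given in days. Protocol 10.9 (Amendment 4) justifies the End-of-Treatment (EoT) visit as the last critical PK/PD "timepoint (5.5 half-lives for study drug").

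**The concern.** An AUC to infinity needs a profile long enough that the extrapolated tail is a small part of the total. If the half-life is near a week, a one-week profile cannot provide that. Two consequences follow. First, the SAP's own rule would leave AUCinf, CL and Vd unsummarized for most participants, although PK parameters serve a secondary objective. Secondly, values that Section 8.3 considers too uncertain to summarize would still enter two analyses in Section 8.4: a power model with a formal conclusion rule, and the denominator of F. The check can also fail the other way. If λz is fitted while distribution is still under way, it is too steep, the estimated tail is too small, and a low AUCinf can pass.

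**Working it through.** **Step 1: implied half-life.** The only stated figure is 5.5 half-lives at EoT. I assume that it is counted from the last SC dose.
- Subsequent participants: (57 − 22)/5.5 = 35/5.5 = 6.36 days.
- First participants: (65 − 29)/5.5 = 36/5.5 = 6.55 days.
- With the EoT window of −3/+7 days, the first figure runs from 32/5.5 = 5.8 to 42/5.5 = 7.6 days. Counted from Day 1 it would be 56/5.5 = 10.2 days, which makes the problem worse.

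**Step 2: one-compartment extrapolation**, 2^(−T/t½).
- Subsequent, T = 7 days: 7/6.36 = 1.10 half-lives; 2^(−1.10) = 47%. Over 5.8 to 7.6 days the range is 43% to 53%.
- First, T = 14 days: 14/6.55 = 2.14 half-lives; 2^(−2.14) = 23% (22% with 6.36 days).
- To stay within 20%, t½ must not exceed 7 × ln 2/ln 5 = 3.0 days for a 7-day profile, or 6.0 days for a 14-day one.

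**Step 3: a bound from Protocol Table 5, not using that half-life.** With linear PK and F ≤ 1, the predicted weekly SC AUC cannot exceed AUCinf(IV). The true unobserved share at 168 h is therefore at least 1 − AUC0-168h(IV)/AUC0-168h(SC).
- 15 mg: 1 − 325/441 = 26%.
- 90 mg: 1 − 1951/2645 = 26%.
- 45 mg as printed: 1 − 1084/1318 = 18%. This row disagrees with its own margin. Against the NOAEL exposure of 36800 in Protocol 6.6.1, 36800/1084 = 34, while Table 5 prints 38. A margin of 38 implies about 968, which gives 1 − 968/1318 = 27%. The other five AUC margins reproduce (113, 83, 28, 19, 14).
- At the 75% SC bioavailability assumed in Protocol 4.3, the 15 and 90 mg bounds become about 45% (for example 1 − 0.75 × 325/441).

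**Step 4: what NCA would report.** The 20% rule acts on the estimated share, not the true one. I built two-compartment IV curves that match the 15 mg row (Cmax 4.3, AUC0-168h 325) with a 6.36-day terminal half-life. I then applied the linear trapezoidal rule at the SAP sampling times, with λz from the last three points.

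| Distribution t½ | Subsequent: estimated share (true) | Estimated t½ | AUCinf error | First: estimated share |
|---|---|---|---|---|
| 12 h | 42% (44%) | 5.8 d | −3% | 20% |
| 24 h | 32% (40%) | 4.4 d | −11% | 17% |
| 36 h | 24% (35%) | 3.5 d | −13% | 13% |
| 48 h | 19% (27%) | 2.9 d | −9% | 7% |

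r² was at least 0.987 throughout, so the 0.80 threshold screens out nothing. In the first three rows the subsequent participants' values are suppressed. In the last they pass, with AUCinf about 9% low. First participants' AUCinf was within 2% of the truth in all four rows.

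**The case against.** The strongest reply is that the SAP largely handles this. Withholding summaries above 20% is the safeguard working. Values are still listed with %AUCextrap, r², the number of points and the λz bounds. Cmax and AUC168h are already in the power model, so IV dose proportionality can be assessed without AUCinf. The PK stopping limit uses Cmax and AUC0-168h, no hypotheses are planned, and the primary endpoint is safety. A proportional bias common to all doses would move only the intercept of the power model, not its slope. All of this stands, and it limits the severity. It does not explain why Section 8.4 omits the condition that Section 8.3 sets. Nor does it protect F: an AUCinf 9% low makes F about 9% high (1/0.915 = 1.09).

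The evidence is also softer than it may look. The half-life is inferred from one clause in an amendment rationale, and Table 5 holds forecasts from animal data. A one-compartment curve through the Table 5 IV Cmax and AUC alone gives a half-life of 61 to 72 h and 15% to 20% extrapolation, inside the limit. For 15 mg, however, that means AUCinf = 325/(1 − 0.152) = 383, below the SC prediction of 441, which linear PK with F ≤ 1 does not allow. The 90 mg row has the same conflict (1951/(1 − 0.149) = 2292 against 2645).

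A reader might infer that the rule removes AUCinf, CL and Vd from every cohort by design. The documents do not support that. First participants have about 2.1 half-lives of IV sampling and an estimated share of about 7% to 23%, depending on the distribution phase.

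**Conclusion.** The point holds, at moderate severity. For about 4 of 5 participants per cohort the IV profile covers about 1.1 implied half-lives, and extrapolation is likely to exceed 20%: about 47% with one compartment and about 19% to 42% by NCA on two-compartment curves. Table 5 puts the true share at no less than 26% for 15 and 90 mg, and 18% for 45 mg as printed. AUCinf, CL and Vd will probably go unsummarized for most participants. A cohort summary could then rest on the first participant alone. With slow distribution, the 20% and r² checks can pass an AUCinf about 9% low.

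The defect to correct is narrower than the short profile: Section 8.4 uses AUCinf in the power model and in F without the condition in Section 8.3. This rests on an inferred half-life, linear PK and F ≤ 1. It does not show that the 20% rule is wrong, or that dose proportionality cannot be assessed.

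**What to change.** In SAP 8.4:
1. Base the IV dose-proportionality conclusion on AUC168h and Cmax.
2. Drop AUCinf from the power model, or restrict it to profiles with %AUCextrap of 20% or less.
3. State that the condition applies profile by profile and wherever AUCinf is used, including the denominator of F. Say what will be reported for F when a profile does not qualify.

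In SAP 8.3, keep AUCinf, CL and Vd in listings beside %AUCextrap, and show the first participants' 14-day IV results separately. Optionally, report t½ from the washout after SC dose 3 and a model-based CL and Vd, as supportive results only. Replacing NCA would depart from Protocol 9.4.3.1. Separately, the Table 5 row for 45 mg IV should be reconciled with its margin.

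I would not add a rule that the λz window must span two estimated half-lives. In the 48 h case above, fits with four or five points span 2.1 to 2.3 half-lives and would pass although biased. In the 12 h case, the accurate first-participant fit spans only 1.6 and would be rejected.

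The cost is a few sentences, with no new samples or participants. The downside is that few or no AUCinf values may remain in the power model, and few in F.

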4.2. Scientific Rationale for Study Design

As this is the first time ALXN1850 will be dosed in humans, an open-label dose escalating design was chosen for initial assessment of the safety, tolerability, PK, and PD of ALXN1850 IV and SC in adults with HPP.

The scientific rationale for each aspect of the study design is discussed below:

- This study will be conducted in adult participants with HPP because ALXN1850 is designed as a TNSALP ERT that is expected to lead to improvement in this patient population. Because of the potential for immunogenicity, this study will enroll adults with HPP who are not anticipated to require continued treatment with ERT, based on their signs and symptoms, and the Investigator's clinical assessment of their current condition.
- A single ALXN1850 IV dose will provide the reference necessary for assessing absolute bioavailability.
- Weekly SC dose will provide the PK and PD information that will support the intended dose regimen in this patient population.
- Three weekly doses of SC ALXN1850 will provide accumulation information for this study drug.
- The qw SC dose range proposed for this study (15 to 90 mg) is expected to cover the therapeutic range in humans.
- An 8-week follow-up will provide enough time to assess immunogenicity and possible risks to the participants.

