9.4.3. Other Analyses

9.4.3.1. Pharmacokinetic Analyses

All PK analyses will be performed on the PK Set and will be reported by each cohort. The individual plasma concentration data from participants who receive ALXN1850 with actual sampling dates and times will be used to derive the PK parameters by noncompartmental analyses methods using Phoenix WinNonlin 8 or higher.

PK Parameters	Definition
C _{max}	Maximum observed plasma concentration
t _{max}	Time to maximum observed plasma concentration
AUCt	Area under the plasma concentration versus time curve from time 0 to the last quantifiable concentration
AUC _{tau}	Area under the plasma concentration versus time curve during the dosing interval
AUC _∞	Area under the plasma concentration versus time curve from time 0 (dosing) to time infinity
t _{1/2}	Terminal elimination half-life
λ _z	Terminal-phase elimination rate constant
CL or CL/F	Total body clearance
Vd or Vd/F	Volume of distribution
R	Subcutaneous accumulation ratio (Dose 3/Dose 1)
F	Absolute bioavailability after subcutaneous administration

The following PK parameters will be derived:

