Individual plasma concentrations of ALXN1850 for each treatment will be presented in data listings and summarized separately using descriptive statistics (N, n [non-missing values within the population], arithmetic mean, SD, %CV, median, minimum, and maximum) by cohort, study day, and scheduled time point. All participants (first and subsequent) will be summarized together for Days 1-8 (predose) for each cohort, after Day 8 only subsequent participants data will be summarized and whereas first participant data will be presented separately. An additional sensitivity analysis will be performed by combining subsequent participants with the first participant (following each SC dosing, ie, SC Dose 1, SC Dose 2, and SC Dose 3) whe re data (corrected from prior carryover exposure post IV dose) is summarized by cohort and scheduled timepoints relative to each dose.

Individual plasma concentrations for ALXN1850 will be plotted for each participant by actual time on both linear and semi-logarithmic scales. Mean plasma concentrations of ALXN1850 versus nominal time will be plotted for each treatment on both linear and semi-logarithmic scales. In addition, mean plasma concentrations of ALXN1850 versus nominal time will be plotted for each treatment by ADA status on both linear and semi-logarithmic scales. The definition of ADA status (ADA negative and ADA positive, and/or pre-existing immunogenicity, treatment-emergent ADA responses, and treatment-boosted ADA responses if data permits, the definition for the ADA response categories is described in the Section 11 of Immunogenicity Analysis).

Individual and mean plasma trough concentrations (C_{trough}) for ALXN1850 versus day following subcutaneous dose administration will be plotted on both linear and semi-logarithmic scales. Time to reach steady state will be graphically assessed by plotting mean plasma C_{trough} concentration versus study day in both linear and semilogarithmic scales.

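### The SC accumulation ratio R in SAP 8.3 does not use the carryover-corrected AUCtau, so residual IV drug would make it too low

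*SAP*

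**What the plan says.** Protocol 9.4.3.1 lists the parameter as "Subcutaneous accumulation ratio (Dose 3/Dose 1", with nothing on carryover. SAP 8.3 makes it specific: "Subcutaneous accumulation ratio (AUC _{tau_SC} 3rd dose / AUC _{tau_SC} 1st dose". The label AUCtau_SC is not itself a row of the parameter table. The table has AUCtau, and separately AUCtau_corrected and Cmax_corrected, the last two "for SC dose only if carryover from IV exposure is observed". All of these are among the parameters "which will be listed and summarized". The table gives no formula for the correction.

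SAP 8.2 also recognises carryover. It plans a sensitivity summary of concentrations "corrected from prior carryover exposure post IV dose", and for the main concentration summary it says that "after Day 8 only subsequent participants data will be summarized and whereas first participant data will be presented separately". SAP 8.3 summarises parameters by treatment and states no such split. It adds only that "Additional plasma PK parameters may be calculated if deemed appropriate".

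Protocol Table 3 places dosing on Days 1, 15, 22 and 29 for the first participant of each cohort and on Days 1, 8, 15 and 22 for the others. The Day 1 dose is IV and the rest are SC, at the same milligram dose within a cohort (Protocol 4.3).

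**The concern.** Accumulation is the protocol's reason for giving three SC doses: "Three weekly doses of SC ALXN1850 will provide accumulation information for this study drug" (Protocol 4.2). A ratio of total areas answers that question only if both areas contain SC drug alone. Here the dose 1 interval begins 7 or 14 days after an IV dose of equal size, and the dose 3 interval begins 14 days later still. Any remaining IV drug therefore adds more to the denominator than to the numerator.

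R would then mix SC accumulation with IV washout. It would also depend on the IV-to-SC gap, which differs between first and subsequent participants by design. With about 5 participants per cohort and at least 3 expected to complete, one participant on the longer gap can shift a cohort summary for reasons of schedule alone. The SAP anticipates carryover elsewhere but does not carry the correction, or the separation of first participants, through to R.

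**Working it through.** The documents give no value of R to reproduce, so the check has two parts: the direction by algebra, and the size by an illustrative model.

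**Direction.** Let d1 and d3 be the SC-only areas over the intervals after SC doses 1 and 3, and c1 and c3 the residual IV areas in the same intervals.

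- R as written = (d3 + c3)/(d1 + c1)
- SC-only accumulation = d3/d1
- R as written is below d3/d1 exactly when c3/c1 < d3/d1.

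With stable first-order elimination at rate k per day, c3/c1 = exp(−14k), which is below 1. SC doses superpose, so d3/d1 is at least 1. The inequality holds whenever c1 > 0, at any half-life. Over 1,000 combinations (half-life 0.5–20 d, F 0.1–1, absorption half-life 0.11–4.07 d), R as written never exceeded the SC-only ratio, and the 7-day-gap value never exceeded the 14-day-gap value.

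**Size: inputs.** Equal IV and SC doses and F = 0.75 (Protocol 4.3); τ = 7 d; gap g = 7 or 14 d (Protocol Table 3). Assumed: one compartment, absorption half-life 1 d (ka = ln 2/1), half-life varied.

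**Formulas**, with IV AUCinf set to 1:

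- AUC_sc(0–T) = 1 − [ka·exp(−kT) − k·exp(−ka·T)]/(ka − k)
- d1 = F·AUC_sc(0–7 d); d3 = F·AUC_sc(0–21 d)
- c1 = exp(−kg) − exp(−k(g+7)); c3 = c1·exp(−14k)

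**Worked case, half-life 3 d** (k = 0.231): d1 = 0.530, d3 = 0.741, so SC-only = 1.40.

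- 7-day gap: c1 = 0.159, c3 = 0.006; R = (0.741 + 0.006)/(0.530 + 0.159) = 1.09, which is 22% low.
- 14-day gap: c1 = 0.032, c3 = 0.001; R = (0.741 + 0.001)/(0.530 + 0.032) = 1.32, which is 5% low.

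| Half-life (d) | SC-only | R, 7-day gap | R, 14-day gap | IV share of dose 1 AUCtau, 7 / 14-day gap |
|---|---|---|---|---|
| 1.2 | 1.07 | 1.05 (−2%) | 1.07 (0%) | 2% / 0% |
| 2.5 | 1.30 | 1.07 (−17%) | 1.26 (−3%) | 18% / 3% |
| 3 | 1.40 | 1.09 (−22%) | 1.32 (−5%) | 23% / 6% |
| 5 | 1.76 | 1.16 (−34%) | 1.47 (−17%) | 37% / 18% |
| 6.4 | 1.97 | 1.22 (−38%) | 1.52 (−23%) | 43% / 26% |
| 8 | 2.16 | 1.29 (−40%) | 1.56 (−28%) | 47% / 32% |

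Linear trapezoids on the scheduled sampling times change little. At 6.4 d they give 1.95 SC-only, 1.20 at the 7-day gap and 1.50 at the 14-day gap.

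**Sensitivity at 2.5–3 d, 7-day gap.** Absorption half-life 0.5–3 d gives R of 1.02–1.40 against 1.21–1.99. F of 0.6–1.0 gives 1.03–1.15 against 1.30–1.40.

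**Which half-life?** The documents do not agree within this model.

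- Solving (1 − exp(−168k))/k = AUC/Cmax, with k per hour, for the IV rows of Protocol Table 5 (325/4.3, 1084/13, 1951/26) gives 2.57, 3.01 and 2.55 d.
- The SC/IV AUC ratios in the same table (441/325 = 1.36, 1318/1084 = 1.22, 2645/1951 = 1.36) need 5.3–8.2 d.
- An Amendment 4 rationale in Protocol 10.9 puts the end-of-treatment visit at 5.5 half-lives without naming the starting dose. Counted from SC dose 3 in subsequent participants, 35/5.5 = 6.4 d.

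**If clearance changes.** Doubling the elimination rate from SC dose 2 on, at the 7-day gap, gives R of 0.54–0.55 against 0.66–0.71 (2.5–3 d) and 0.62–0.77 against 0.97–1.34 (5–8 d). The direction is the same in that example, but neither ratio then measures accumulation alone.

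**The case against.** The strongest reply is that the SAP never says AUCtau_SC is uncorrected. The label is undefined, and a table that creates a corrected SC area for exactly this case could be read as using it wherever SC areas are compared. On that reading there is no bias. This stands as a statement of ambiguity. However, the R row does not name the corrected parameter that sits in the same table, and the only stated use of a correction outside the parameter table is a concentration sensitivity summary. A programmer following the text would compute an uncorrected R.

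It can also be said that the corrected areas will be listed, so a reader could form the ratio. That helps only once the correction is defined, and it is not.

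Three further points are fair:

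- R is descriptive and enters no escalation or stopping rule.
- The size is not anchored, because the half-life is unsettled.
- A corrected R depends on λz, which may be hard to estimate. In the model at 2.5–3 d, concentrations 5 weeks after SC dose 3 are 0.02–0.07% of Cmax. If the quantification limit were 0.1% of Cmax (an assumption; none is stated), a late sampling window would almost always miss the SAP's three-point minimum. With two-compartment disposition a simple correction over-corrects by about 4–8%, though it stays nearer the truth than the uncorrected ratio.

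These points bear on priority and on how the correction is built. They do not remove the need to say which AUCtau R uses. The same ambiguity touches the other uses of plain AUCtau in SAP 8.3 and 8.4, including F.

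**Conclusion.** The concern holds, as a minor point. The textual gap is certain: R is defined without reference to the corrected AUCtau, and the correction has no formula. The direction of the bias is certain under three conditions: IV carryover is present, AUCtau_SC is uncorrected, and clearance is stable. Unequal bias between first and subsequent participants then follows from the two dosing gaps.

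The size rests on a one-compartment model, F of 0.75 and an assumed absorption half-life of 1 day. It runs from negligible at a half-life near 1 day to about 40% low at 8 days with the 7-day gap. From 2.5 to 8 days, SC accumulation of 1.3- to 2.2-fold would appear as 1.07- to 1.29-fold in subsequent participants. Anti-drug antibodies, which Protocol 2.3.1 names as a risk, could alter clearance, and the direction is then not guaranteed.

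**What to change.** In SAP 8.3, define R as AUCtau_corrected (SC dose 3) divided by AUCtau_corrected (SC dose 1) when carryover is observed, and say that AUCtau is used otherwise. State how AUCtau_corrected is computed. One option, with C_pre the concentration before SC dose 1:

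- from the SC dose 1 AUCtau subtract C_pre·(1 − exp(−λz·τ))/λz;
- from the SC dose 3 AUCtau subtract the same term times exp(−2·λz·τ).

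On the scheduled sampling times without noise this returns 1.29–1.39 at 2.5–3 d and 1.74–2.14 at 5–8 d, against SC-only trapezoid values of 1.30–1.39 and 1.75–2.14. Keep the uncorrected ratio as a sensitivity result that does not pool first with subsequent participants; the single first participant per cohort can be listed. The sponsor should prespecify what counts as observed carryover, the source of λz, and the fallback when λz cannot be estimated. Stating the rule once for every use of SC AUCtau would avoid leaving the same question open for F.

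The cost is SAP wording and one derivation rule, with no new samples. The corrected ratio is noisier. With an assumed 15% sample noise, and λz taken from 168 h to 8 weeks after SC dose 3 with no quantification limit applied, the per-participant CV at the 7-day gap rises from about 12% to 13–15% (2.5–3 d) or 19–23% (5–8 d). At the 14-day gap it rises to about 13% or 14–16%. If absorption is slower than elimination (half-life 2.5 d, absorption half-life 3 d), the correction overshoots slightly at the 7-day gap: 1.89 against a true 1.80, with 1.37 uncorrected. Late clearance altered by antibodies would also affect it.
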